3.1 OVERVIEW

This is a phase I, randomised, double-blind, placebo-controlled study to investigate the safety, tolerability, and PK of AX-158 in healthy male participants following single (Part A) and multiple (Part C) ascending doses including food effect (Part B).

The study will be conducted in three parts:

Part A

Part A (SAD) will enrol up to 8 participants per cohort randomised (3:1) to receive AX-158 or placebo. Part A will follow a single ascending dose (SAD) design with all participants receiving one dose of AX-158 (or placebo) in the fasted state.

This part will be conducted in up to 34 participants (8 participants in cohorts 1 and 5, 6 participants in cohorts 2, 3 and 4). An additional two cohorts of up to eight (8) participants each (up to 16 additional participants total) may be investigated if required.

Part B

Part B (Food Effect) will be conducted in up to 8 participants in a cross-over manner; each participant will receive AX-158 in the fed and fasted state.

This part will be conducted in up to 8 participants in a cross-over manner.

Part C

Part C (MAD) will enrol up to 8 participants per cohort randomised to (3:1) to receive AX-158 or placebo. Part C will follow a multiple ascending dose (MAD) design with participants receiving AX-158 (or placebo) once daily for 10 consecutive days, in a fed or fasted state (depending on the outcome of the Part B (Food Effect)). Doses, dosing duration and dose regimen (i.e., q.i.d., b.i.d., t.i.d.) of AX-158 and matching placebo for Part C may be modified based on all available safety, tolerability, and PK data and applied to additional MAD cohorts.

This part will be conducted in up to twenty-four (24) participants (3 cohorts of up to 8 participants). An additional two cohorts of up to eight (8) participants each (up to 16 additional participants total) may be investigated if required.

Duration of study:

- Part A: approximately 6 weeks for each individual (from the screening to post-study follow-up).
- Part B: approximately 8 weeks for each individual (from the screening to post-study follow-up).
- Part C: approximately 7 weeks for each individual (from the screening to post-study follow-up).

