4.2 SECONDARY VARIABLES

The secondary plasma pharmacokinetic (PK) endpoints for this study are as follows:

- C_{\max} Maximum observed concentration

Version: 3.0
Document Title: SAP Template - Phase 1
Document Number: TEMP-00109
Previous Document Number: STATt008

• T_{max}	Time to maximum observed concentration
• T_{lag}	The delay in achieving T_{max} (only in Part B)
• k_{el}	Elimination rate constant
• $t_{1/2}$	Terminal elimination half-life
• AUC_{0-24}	Area under the concentration-time curve (AUC) from the time of dosing to 24 hour post dose
• $AUC_{0-\tau}$	If part C dosing is not q.d.
• AUC_{0-t}	Area under the concentration-time curve (AUC) from the time of dosing to the time of the last measurable concentration
• $AUC_{0-\infty}$	AUC extrapolated to infinity
• $AUC_{\% \text{ extrapolated}}$	Residual area
• CL/F	Apparent total body clearance
• Vz/F	Apparent volume of distribution

The secondary urine PK endpoints for Part C of this study are:

• A_e	Amount and cumulative amount of dose excreted in urine over each collection interval
• $A_e\%$	% and cumulative % of dose excreted in urine over each collection interval
• CL_R	Renal clearance

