AUC_{0-24} ($\text{h}^*\mu\text{g/mL}$)	Area under the concentration-time curve (AUC) from the time of dosing to 24 h post-dose	AUC measured from the concentration at time of dosing to 24 hours post dose. The AUC is computed using the linear up-log down trapezoidal rule.	AUC0-24
$AUC_{0-\tau}$ ($\text{h}^*\mu\text{g/mL}$) (only required if non-q.d. dosing regimen)	Area under the plasma concentration-time curve (AUC) from the time of dosing to $<X>$ hours (dosing interval) after the Day $<X>$ dose.	AUC measured from the concentration at time of dosing to the concentration at $<X>$ hours. The AUC is computed using the linear up-log down trapezoidal rule.	AUC_TAU

Part C on Final Dosing Day:

Pharmacokinetic Parameter and Unit	Definition	Computation	WinNonlin Parameter Name
C_{max} ($\mu\text{g/mL}$)	Maximum concentration.	Maximum observed concentration, occurring at T_{max} . If not unique, then the first maximum is used.	Cmax
T_{max} (h)	The time to maximum observed concentration.	Time of maximum observed concentration. If the maximum observed concentration is not unique, then the first maximum is used.	Tmax

Pharmacokinetic Parameter and Unit	Definition	Computation	WinNonlin Parameter Name
λz (1/h)	Elimination rate constant.	First order rate constant associated with the terminal (log-linear) portion of the curve. Estimated by linear regression of time vs. log concentration; the regression analysis should contain data from at least 3 different time points in the terminal phase	lambda_z
$t_{1/2}$ (h)	Terminal elimination half-life.	$= \ln(2) / \lambda z$	HL_Lambda_z
AUC_{0-24} (h* μ g/mL)	Area under the concentration-time curve (AUC) from the time of dosing to 24 h post-dose	AUC measured from the concentration at time of dosing to 24 hours post dose. The AUC is computed using the linear up-log down trapezoidal rule.	AUC0-24
$AUC_{0-\tau}$ (h* μ g/mL) (only required if non-q.d. dosing regimen)	Area under the plasma concentration-time curve (AUC) from the time of dosing to 24 hours (dosing interval) after the Day 10 dose.	AUC measured from the concentration at time of dosing to the concentration at 24 hours. The AUC is computed using the linear up-log down trapezoidal rule.	AUC_TAU

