11.4.3.4 Part C (MAD) - Accumulation

For each dose level, log-transformed C_{\max} and $AUC_{0-\tau}$ (only applicable if non-q.d. dosing regimen is implemented) values on Day 1 and Final Dosing Day (Day 10) will be subjected to an ANOVA with study day as a fixed effect and subject as a random effect. For comparison, point estimates and 90% CIs for the difference between Day 10 and Day 1 will be constructed using the residual mean square error obtained from the ANOVA for each dose level. The point and interval estimates will then be back transformed to give estimates of the ratios of the geometric LSMeans and corresponding 90% CIs. In addition, estimated geometric LSMeans and corresponding 95% CIs will be presented for each study day.

The geometric LSMean ratios and corresponding 90% CIs for C_{\max} and $AUC_{0-\tau}$ will be represented graphically (a plot with error bars) with all dose levels on one graph, one graph per parameter. On the same graph, points indicating individual within-subject ratios will be presented.

Statistical analysis of PK parameters will be performed using the PK set.

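### If a Part C cohort is not dosed once daily, the SAP fixes AUC0-tau at 24 h on the Final Dosing Day but at the dosing interval on Day 1, so the AUC accumulation ratio would compare unequal windows

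*SAP*

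**What the plan says.** Part C is planned with "participants receiving AX-158 (or placebo) once daily for 10 consecutive days" (SAP 3.1). The same section allows the regimen to change to b.i.d., t.i.d. or q.i.d. for additional cohorts, and protocol 10.2 lists this among the changes that need no substantial amendment.

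AUC0-tau belongs to that contingency. SAP 4.2 lists it with the condition "If part C dosing is not q.d". In the SAP 11.4.2 tables for Part C, both the Day 1 row and the Final Dosing Day row carry the condition "only required if non-q.d. dosing regimen". The two rows then differ:

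- Day 1, computation: "AUC measured from the concentration at time of dosing to the concentration at $<X>$ hours". The definition column labels this time as the dosing interval.
- Final Dosing Day, definition: "Area under the plasma concentration-time curve (AUC) from the time of dosing to 24 hours (dosing interval) after the Day 10 dose".
- Final Dosing Day, computation: "AUC measured from the concentration at time of dosing to the concentration at 24 hours".

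Both tables also contain a separate AUC0-24 row.

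SAP 11.4.3.4 takes Cmax and AUC0-tau forward to the accumulation analysis, the latter "only applicable if non-q.d. dosing regimen is implemented) values on Day 1 and Final Dosing Day (Day 10) will be subjected to an ANOVA". The Day 10 minus Day 1 difference on the log scale is back-transformed to a ratio with a 90% CI, reported in Table 14.4.2.6 and Figure 14.4.2.4.

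**The concern.** The Final Dosing Day row contradicts its own condition. It applies only when dosing is not once daily, and in that case 24 h is not the dosing interval. It also departs from the SAP glossary, which ties AUC0-tau to a single dosing interval, and from protocol 10.11.8, where tau is the dosing interval and 0 to 24 h is given only as the planned case.

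If the table is programmed as written, the numerator of the accumulation ratio covers two to four dosing intervals and the denominator covers one. Part of the ratio would then reflect the integration window and not drug accumulation. The distortion runs in the same direction in every participant, so neither the point estimate nor its confidence interval would reveal it.

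**Working it through.** The plan states no accumulation figure, so there is nothing to reproduce. The check has two steps: compare the windows, then illustrate the size.

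**Windows.** The regimens come from SAP 3.1. The intervals assume equally spaced doses: 24/2 = 12 h, 24/3 = 8 h, 24/4 = 6 h.

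| Regimen | AUC0-tau derived? | Day 1 window | Final Dosing Day window as written | Length ratio |
|---|---|---|---|---|
| q.d. | No | – | – | – |
| b.i.d. | Yes | 12 h | 24 h | 2 |
| t.i.d. | Yes | 8 h | 24 h | 3 |
| q.i.d. | Yes | 6 h | 24 h | 4 |

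This step needs no pharmacokinetic assumption beyond reading the Day 1 placeholder as its label says.

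**Size.** The documents give no human half-life. Assumptions: linear one-compartment oral model, absorption rate ka = 1/h, half-life 2 to 24 h, k = ln 2 / half-life. The single-dose profile is proportional to ka/(ka − k) × (exp(−kt) − exp(−ka·t)). Doses are superimposed every tau hours from time 0, with the Day 10 morning dose at 9 × 24 = 216 h.

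- Equal-window ratio = AUC(216, 216 + tau) / AUC(0, tau)
- Ratio as written = AUC(216, 240) / AUC(0, tau)
- Inflation = ratio as written / equal-window ratio = AUC(216, 240) / AUC(216, 216 + tau)

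If dosing continues through the 24 h, then at steady state the numerator holds 24/tau identical intervals, so the inflation is 24/tau: 2.00, 3.00 and 4.00. The numerical model gave these values at every half-life tried.

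If the Day 10 morning dose is the last, the inflation depends on the half-life:

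| Regimen | 2 h | 4 h | 8 h | 12 h | 24 h |
|---|---|---|---|---|---|
| b.i.d. | 1.02 | 1.15 | 1.39 | 1.53 | 1.73 |
| t.i.d. | 1.10 | 1.38 | 1.82 | 2.09 | 2.47 |
| q.i.d. | 1.22 | 1.63 | 2.27 | 2.66 | 3.21 |

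Hand check, ignoring the absorption phase: inflation = (1 − exp(−24k)) / (1 − exp(−tau·k)). For b.i.d. this reduces to 1 + exp(−12k), which is 1 + 1/64 = 1.02 at a 2 h half-life, 1 + 1/2 = 1.50 at 12 h and 1 + 0.71 = 1.71 at 24 h. These are close to the model values.

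Example, b.i.d. with a 12 h half-life: the equal-window ratio is 2.13. As written it would be 3.26 if the morning dose is the last (3.26/2.13 = 1.53), or 4.26 if dosing continues (4.26/2.13 = 2.00).

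**The case against.** The best defence is that the row is leftover once-daily text and that no one would follow it. The glossary and the protocol define the interval correctly. A 24 h AUC0-tau would merely duplicate the AUC0-24 row in the same table. The Day 1 row is an unfilled placeholder that must be completed before any use, and the shell notes say the once-daily treatment footnotes should be amended if the regimen changes. Nothing goes wrong under the planned regimen.

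Most of this stands, and it limits the point. The error is contingent on two events: a cohort is dosed other than once daily, and the row is followed literally. But a regimen change is an expected adaptation, and the row was written solely for it. The shell notes cover the treatment footnotes and not the AUC definition. A placeholder prompts someone to fill it in, whereas a hard-coded 24 hours in two columns does not.

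Two stronger readings are tempting but not supported:

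- A reader might take 2, 3 or 4-fold as the expected inflation. That needs dosing to continue after the Day 10 morning dose. The Part C shells place the final dose on the morning of Day 10 (in footnotes worded for once-daily dosing), and SAP 11.4.1 and 11.4.2 sample to 72 h after Day 10 dosing and derive a terminal half-life, which fits a last dose that morning. With a short half-life and b.i.d. dosing the inflation could be negligible.
- A reader might infer bias in the Part C dose-proportionality slope (SAP 11.4.3.2). That analysis is specified for Day 1 and Day 10 and makes no comparison between days. If a window multiplies every AUC by a constant m, the power model becomes log(AUC) = (α + log m) + β log(dose): the intercept moves and the slope does not. No slope bias is shown.

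**Conclusion.** The Final Dosing Day definition of AUC0-tau is wrong as written, contingent on a Part C cohort that is not dosed once daily. In that case, and if the table is followed literally, the AUC accumulation ratio compares a 24 h window with one of 12, 8 or 6 h. With the Day 10 morning dose as the last, the inflation is about 1.02 to 1.7 (b.i.d.), 1.1 to 2.5 (t.i.d.) and 1.2 to 3.2 (q.i.d.). These ranges rest on linear one-compartment kinetics, an assumed absorption rate of 1/h and assumed half-lives of 2 to 24 h. The window mismatch itself rests only on the text and on equally spaced doses.

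A reader might conclude that the trial's accumulation result is compromised as planned. The documents do not support that. Under once-daily dosing the AUC part of the analysis does not arise ("only applicable if non-q.d. dosing regimen is implemented"). Cmax, the other accumulation variable, is unaffected under any regimen. PK is a secondary objective, and the protocol plans no formal hypothesis testing.

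**What to change.** In the Final Dosing Day table of SAP 11.4.2, replace 24 hours with `<X>` hours (the actual dosing interval) in both the definition and the computation of AUC0-tau, matching the Day 1 row. State in SAP 11.4.3.4 that the same window is used on both days. Leave AUC0-24 as the separate parameter it already is.

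The cost is one table row and one sentence, to be made before the SAP is finalised ahead of database lock. No further sampling times are needed: SAP 11.4.1 already schedules plasma samples at 6, 8 and 12 h on Day 1 and Day 10.

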Participants will be admitted to the Clinical Unit on the morning of Day-1 with confirmation of eligibility and baseline assessments performed as per Table 10.9.3. Randomisation will occur prior to dose on Day 1. An evening snack will be consumed at least 10 h before each dose administration. After an overnight fast of at least 10 h, dose administration will occur each day, on the morning of Day 1 to Final Dosing Day (planned as Day 10). It is planned to administer doses in Part C in a fasted state, however following review of Part B food-effect data, the dose *may* be administered in a fed state with a standardised meal. Fasting will continue until 4 h post-dose; a standardised meal will then be provided. Clinical and laboratory assessments of safety, tolerability and PK variables will be conducted throughout the in-house period as per Table 10.9.3.

Participants will be discharged from the Clinical Unit on Post-Treatment (i.e., Day 13) following the completion of the 72 h post-last dose assessments providing there are no ongoing safety concerns.

Post-Study Follow Up Visit (5-7 days after final dose of IMP i.e., Day 17).

For participants in all MAD cohorts, a follow-up visit will be conducted 5-7 days following last IMP or placebo administration. If all follow-up assessments (Table 10.9.3.) are satisfactory the PI (or delegate), will discharge the participant from the study. If any AEs are ongoing, or any assessments are not satisfactory, participants may be recalled to the unit for follow-up assessments until the PI (or delegate) is satisfied the participant is medically stable and may be discharged from the study. Participants will be advised to return or contact the unit at any time if they may be experiencing any adverse effects.

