10.11.2 Study Variables/Endpoints

Part A (SAD):

The following plasma PK endpoints will be derived: C_{max} , T_{max} , λz , $t_{1/2}$, AUC_{0-24} , AUC_{0-t} , AUC_{0-inf} , $AUC_{\%extrapolated}$, CL/F , Vz/F .

Part B (Food Effect):

The following plasma PK endpoints will be derived: C_{max} , T_{max} , T_{lag} , λz , $t_{1/2}$, AUC_{0-24} , AUC_{0-t} , AUC_{0-inf} , $AUC_{\%extrapolated}$, CL/F , Vz/F .

Part C (MAD):

The following plasma PK endpoints will be derived on Day 1: C_{max} , T_{max} and AUC_{0-24} , (AUC_{0-t} will also be derived if dosing interval other than q.d).

The following plasma PK endpoints will be derived on Final Dosing Day : C_{max} , T_{max} , λz , $t_{1/2}$, AUC_{0-24} , ($AUC_{0-\tau}$ will also be derived if dosing interval other than q.d.), AUC_{0-t} , AUC_{0-inf} , $AUC_{\text{extrapolated}}$, CL/F and Vz/F .

The following urine PK parameters will be derived on Day 1 and Final Dosing Day: Ae , $Ae\%$, CL_R .

Safety endpoints:

- AEs.
- Laboratory safety (biochemistry, haematology, coagulation, and urinalysis).
- Vital signs (systolic/diastolic blood pressure, heart rate, oral body temperature and respiratory rate).
- 12-lead ECG (Heart rate, PR interval, QRS width, RR interval, QT interval and QT interval corrected using Fredericia's formula (QTcF)).

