11.4 PK ANALYSES

11.4.1 Concentration Data

Plasma PK samples will be collected for the measurement of AX-158 at the following time points:

Part A:

- Day 1 pre-dose, 30 mins, 45 mins, 1h, 2h, 3h, 4h, 6h, 8h, 12h
- Day 2: 24h, 36h
- Day 3: 48h
- Day 4: 72h

Part B: For both treatment periods

- Day 1 pre-dose, 30 mins, 45 mins, 1h, 2h, 3h, 4h, 6h, 8h, 12h
- Day 2: 24h, 36h
- Day 3: 48h
- Day 4: 72h

Part C:

- Day 1 and Day 10 pre-dose, 1h, 2h, 3h, 4h, 5h, 6h, 8h, 12h
- Day 2 and Day 11: 24h, 36h
- Day 3 and Day 12: 48h
- Day 4 and Day 13: 72h
- Day 5: pre-dose
- Day 6: Pre-dose
- Day 7: Pre-dose
- Day 8: Pre-dose

Plasma AX-158 concentrations will be listed along with blood sampling times and details of any sampling time deviations and summarised for each treatment using the descriptive statistics N, n, arithmetic mean,

geometric mean, arithmetic standard deviation (SD), coefficient of variation (CV%), minimum, median and maximum.

The individual subject plasma AX-158 concentration profiles over time will be presented graphically on both linear and semi-logarithmic scales with each subject on a separate plot. For Part C, Day 1 and Final Dosing Day (Day 10) profiles will be presented on the same plot. The geometric mean plasma AX-158 concentration profiles over time will be presented graphically on both linear and semi-logarithmic scales with all treatments on the same plot, with separate plots for Day 1 and Final Dosing Day profiles for Part C.

Urine PK samples will be collected for the measurement of AX-158 at the following time intervals: pre-dose and in intervals of 0-12, 12-24, 24-48 and 48-72 h post-dose on Day 1 and Day 10.

Urine AX-158 concentrations will be listed along with urine volumes and summarised for each treatment using the descriptive statistics N, n, arithmetic mean, geometric mean, arithmetic standard deviation (SD), coefficient of variation (CV%), minimum, median and maximum.

For inclusion within the summary tables and plots, plasma and urine concentrations below the lower limit of quantification (LLOQ) will be imputed as zero at pre-dose and as LLOQ/2 for post-dose samples. They will be listed as recorded. Data reported as not reportable or no sample/result will be handled as missing (i.e. no assumption will be made about the actual concentration).

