AUC_{0-t} (h* μ g/mL)	Area under the concentration-time curve (AUC) from the time of dosing to the time of the last measurable concentration.	AUC measured from the concentration at time of dosing to the last measurable positive concentration. The AUC is computed using the linear up-log down trapezoidal rule.	AUClast
$AUC_{0-\infty}$ (h* μ g/mL)	AUC extrapolated to infinity.	AUC measured from the concentration at time of dosing extrapolated to infinity based on the last observed concentration. $= AUC_{0-t} + \frac{C_{lastobs}}{\lambda z}$	AUCINF_obs
$AUC_{\text{extrap.}}\ (%)$	Percentage of $AUC_{0-\infty}$ due to extrapolation from last observed	Percentage of $AUC_{0-\infty}$ due to extrapolation from time of last measurable positive concentration to infinity.	AUC_%Extrap_obs

Pharmacokinetic Parameter and Unit	Definition	Computation	WinNonlin Parameter Name
	concentration to infinity.	$= \frac{AUC_{0-inf} - AUC_{0-t}}{AUC_{0-inf}} \cdot 100$	
CL/F (L/h)	Apparent total body clearance, calculated as Dose / AUC _{0-inf} .	$= Dose / AUC_{0-inf}$	CL_F_obs
Vz/F (L)	Apparent Volume of Distribution during the terminal phase.	$= \frac{Dose}{\lambda z \cdot AUC_{0-inf}}$	Vz_F_obs
λz lower (listed only)	Elimination rate constant lower limit.	Lower limit on Time for values to be included in the calculation of λz	Lambda_z_lower
λz upper (listed only)	Elimination rate constant upper limit.	Upper limit on Time for values to be included in the calculation of λz	Lambda_z_upper
No. points λz (listed only)	Number of points used for elimination rate constant.	Number of points used for elimination rate constant	No_points_Lambda_z
R ² adjusted (listed only)	R ² adjusted.	Goodness of fit statistic for the terminal elimination phase, adjusted for the number of points used in the estimation of λz	Rsq_adjusted

The terminal elimination rate constant (λz) will be calculated by log-linear regression of the terminal portion of the concentration-time curve only where there are sufficient data i.e. at least 3 time points excluding C_{max} and adjusted R² is greater than or equal to 0.85; lower adjusted R² values may be acceptable at the discretion of the PK analyst if the elimination phase is clearly defined by the profile, values lower than 0.85 will be flagged within the data listing. If these criteria are not fulfilled, parameters dependent on k_{el} for calculation will not be reported.

The following urine PK parameters will be calculated:

Part C on Day 1 and Final Dosing Day

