Pharmacokinetic Parameter and Unit	Definition	Computation	WinNonlin Parameter Name
Ae (µg)	Cumulative amount of study drug excreted in urine during a time interval.	The sum of the individual urine volume * urine concentration of study drug. $= \Sigma (\text{Concentration} \cdot \text{Volume})$	N/A (calculated using SAS)
Ae% (%)	Percentage of study drug excreted in urine during a time interval.	$= 100 \cdot Ae / \text{Dose}$	N/A (calculated using SAS)
CLR (L/h)	Renal clearance.	$= Ae / AUC_{0-t}$	N/A (calculated using SAS)

The derived urine pharmacokinetic parameters Ae, Ae%, CumAe, CumAe%, CLR will be determined from the individual urine concentration versus time data using SAS EG v8.3 or higher.

Derived PK parameters will be listed along with the points used to calculate λz (lower, upper, and number used) and coefficient of determination (R^2) adjusted. The derived PK parameters will also be summarised. The descriptive statistics presented will be N, n, arithmetic mean, geometric mean (with the exception of T_{\max}), SD, coefficient of variation (CV%), minimum, median, and maximum.

Any $AUC_{\% \text{ extrap}}$ values greater than 20% will be flagged within the data listing. In accordance with regulatory guidance, the associated data should not be excluded from analysis but if this is observed for >20% of the profiles, the validity of the study may be in question.

In the instance of a significant sample time deviation ($\geq 5\%$ of nominal time i.e. 72 min) for the 24 h PK sample, the AUC_{0-24} values will be excluded from statistical analysis, but will be calculated, included in the derived PK data listing and flagged. Where a non-significant sample time deviation (≤ 72 min) for the 24 h PK sample occurs and the terminal elimination rate constant (λz) is estimable, this will be used to estimate AUC_{0-24} . Where a non-significant sample time deviation (≤ 72 min) for the 24 h PK sample occurs and the terminal elimination rate constant (λz) is not estimable, WNL is unable to estimate AUC_{0-24} . Therefore, in order for an AUC_{0-24} value to be estimated, the actual sampling time (including bleed time deviations) at the 24 h nominal time point will be used for the partial AUC settings.

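### Part C Day 1 cumulative Ae% runs to 72 h under daily dosing, so its 48 h and 72 h values set urine from two and three doses against one

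*SAP*

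**What the plan says.** The urine parameter table in SAP 11.4.2 is headed "Part C on Day 1 and Final Dosing Day". It describes Ae% as "Percentage of study drug excreted in urine during a time interval", computed as 100 × Ae/Dose, and CLR as Ae/AUC0-t. The sentence below the table reads: "The derived urine pharmacokinetic parameters Ae, Ae%, CumAe, CumAe%, CLR will be determined from the individual urine concentration versus time data". SAP 4.2 makes these secondary endpoints for Part C and describes Ae% as the percentage "and cumulative % of dose excreted in urine over each collection interval". Protocol 10.11.8 defines it in the same way.

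SAP 11.4.1 sets the urine schedule: "pre-dose and in intervals of 0-12, 12-24, 24-48 and 48-72 h post-dose on Day 1 and Day 10".

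Protocol 10.1 sets the dosing: "dose administration will occur each day, on the morning of Day 1 to Final Dosing Day (planned as Day 10"). SAP 3.1 agrees that dosing is once daily for ten days.

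For plasma on Part C Day 1, SAP 11.4.2 lists Cmax, Tmax, AUC0-24 and AUC0-tau, the last marked "only required if non-q.d. dosing regimen". AUC0-t is not in that table.

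**The concern.** Cumulative percentage of dose is normally read as urinary recovery of the dose just given. That reading works after a single dose, or within one dosing interval. Part C has no dose-free gap after Day 1: the 24–48 h collection follows the Day 2 dose and the 48–72 h collection follows the Day 3 dose. If all of this urine is added up and divided by one dose, the result is not the recovery of that dose.

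Nothing in either document limits Day 1 cumulation to 24 h or says that Dose becomes the total given. The shell does not settle it, because the derived urine table (14.4.2.8) has no layout of its own and only points to the plasma table. Two programmers could follow the text and report 72 h values that differ exactly threefold. At stake is the reported extent of renal excretion, a named secondary endpoint that is to be summarised.

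**Working it through.** The plan states no figure for this point, so there is none to reproduce.

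**Inputs.** Doses at 0, 24, 48 h and so on after the Day 1 dose (Protocol 10.1, SAP 3.1). Urine windows 0–12, 12–24, 24–48 and 48–72 h (SAP 11.4.1). Ae% = 100 × Ae/Dose (SAP 11.4.2). The human half-life is not given, so 2 to 96 h is assumed.

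**Step 1: doses given before the end of each cumulative Day 1 window.**
- 0–12 h: 1
- 0–24 h: 1
- 0–48 h: 2 (Days 1 and 2)
- 0–72 h: 3 (Days 1 to 3)

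This count is exact and needs no pharmacokinetic assumption.

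**Step 2: size of the overstatement.** Assume linear one-compartment kinetics with instant input. The share of eventual urinary excretion completed t hours after a dose is F(t) = 1 − exp(−kt), with k = ln 2/half-life. The ratio of cumulative Ae% under daily dosing to its single-dose value is

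R(T) = Σ F(T − d)/F(T), summed over doses at times d < T.

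The fraction excreted cancels. With x = exp(−24k):
- R(24) = 1
- R(48) = 1 + 1/(1 + x)
- R(72) = 1 + (2 + x)/(1 + x + x²)

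Example with a 24 h half-life: x = 0.5, R(48) = 1 + 1/1.5 = 1.667, R(72) = 1 + 2.5/1.75 = 2.429.

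| Half-life (h) | R(24) | R(48) | R(72) |
|---|---|---|---|
| 2 | 1.000 | 2.000 | 3.000 |
| 4 | 1.000 | 1.985 | 2.984 |
| 12 | 1.000 | 1.800 | 2.714 |
| 24 | 1.000 | 1.667 | 2.429 |
| 48 | 1.000 | 1.586 | 2.227 |
| 96 | 1.000 | 1.543 | 2.115 |

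As x goes from 0 to 1, R(48) falls from 2.0 to 1.5 and R(72) from 3.0 to 2.0, so the overstatement does not vanish at any half-life. Adding first-order absorption (0.5 to 2 per hour, half-life 4 to 48 h) gives 1.56–1.98 and 2.19–2.98. With a short half-life, the reported percentage would exceed 100% once the true fraction excreted is above about 1/2 (48 h) or 1/3 (72 h).

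**Step 3: the other reading of Dose.** If Dose meant the sum of doses given, the values in Step 2 are divided by 2 and by 3. The result is 0.75–1.0 of single-dose recovery at 48 h (1.5/2 to 2.0/2) and 0.67–1.0 at 72 h (2.0/3 to 3.0/3).

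**Step 4: CLR, by comparing passages.** The CLR row divides by AUC0-t, but the Part C Day 1 plasma table has no such row. Protocol 10.11.2 attaches the phrase "will also be derived if dosing interval other than q.d" to AUC0-t for Day 1 and to AUC0-tau for the final dosing day, so t may be a misprint for tau. Protocol 10.11.8 gives tau as 0–24 h as planned, and AUC0-24 is derived. On either reading the urine window for Ae is missing. When windows match, Ae0-24/AUC0-24 recovers the true CLR to within 1.00–1.03 with the scheduled samples (absorption and half-life range as in Step 2).

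**Step 5: Day 10.** Ten daily doses have been given and none follows. With instant input, Ae0-24 = (1 − x¹⁰) × fe × Dose, where fe is the fraction excreted in urine. Ae0-72 = (1 − x¹⁰)(1 + x + x²) × fe × Dose. At a 48 h half-life (x = 0.707) these are 0.97 and 0.97 × 2.207 = 2.14 times fe × Dose. With absorption and half-lives of 4 to 48 h the ranges are 0.97–1.00 and 1.02–2.17. The 0–24 h value is close to the fraction sought; the 0–72 h value adds carry-over from earlier doses.

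**The case against.** The best defence is that Dose is undefined rather than wrongly defined, and that cumulative excretion in a multiple-dose part can be read as plain description. That is fair as far as it goes: the 2 to 3 fold figure depends on dividing by one dose. But SAP 4.2 speaks of dose in the singular, the SAP assigns the calculation to SAS, so the written formula is the specification, and the alternative reading does not give single-dose recovery either.

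A second defence is that the SAP follows the protocol's definition. It does, which is why the correction should be logged as a change. SAP 1.1 also says it was written to protocol version 5.0, while the protocol supplied stops at 4.0. The SAP alone (3.1, 4.2, 11.4.1, 11.4.2) is enough for the main point.

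A reader might infer three stronger things that the documents do not support:
- That Ae% has no urine window at all. SAP 4.2 and 11.4.1 name the collection intervals. What is missing is a rule tying Day 1 cumulation to one dosing interval, and a window for CLR.
- That Day 1 CLR will be several times too high. This would need 0–72 h urine over AUC0-24, a pairing that no passage instructs.
- That other regimens are mishandled too. Dosing more than once daily is only an option in SAP 3.1.

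**Conclusion.** Wrong as written, and worth correcting before programming is final. Under planned once-daily dosing, Day 1 cumulative Ae% taken against one dose is overstated by 1.5–2.0 at 48 h and 2.0–3.0 at 72 h. The dose count is exact; the ratios rest on linear kinetics and an assumed half-life range. Values to 24 h are correct. For CLR the urine window and the AUC need stating, and no error size is claimed.

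The impact is confined to descriptive secondary urine PK in Part C. Urine parameters enter none of the statistical analyses in SAP 11.4.3, and no primary endpoint or dosing decision depends on them. The fraction excreted is unknown, so the absolute effect could be small. Correct values can be recomputed from the urine concentrations and volumes.

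**What to change.** In SAP 11.4.2, under once-daily dosing:
- **Day 1:** base Ae% and cumulative Ae% against the single dose on 0–24 h urine only. Set CLR = Ae0-24/AUC0-24.
- **Day 1, later urine:** report 24–48 h and 48–72 h as separate intervals, labelled as following the Day 2 and Day 3 doses, and do not cumulate them against the Day 1 dose.
- **Day 10:** base Ae% on 0–24 h, report 24–72 h descriptively with a note on carry-over, and use the same window for urine and plasma in CLR.
- **CLR row:** state whether t means the last measurable time or tau.
- **Other regimens, if adopted:** match the urine window, the total dose given in it and the AUC over the same interval.

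Record the departure from the protocol definition in SAP 1.2. The cost is small edits to the SAP and the SAS derivation. The 0–12 h and 12–24 h collections and AUC0-24 already exist on both days, so no new samples are needed.
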